The randomization will be integrated into a central Interactive Voice Response System (IVRS) that will be used by the sites to randomize each patient to a treatment condition. For quality control purposes, a second statistician not affiliated with the study will validate the randomization scheme and its transfer to the IVRS randomization database. The IVRS is maintained by the central randomization service, which will provide daily enrollment updates (without treatment assignment indicated) to the DCC project management team. The DCC statistician will review the randomization data on regular basis to ensure that the scheme is being implemented according to plan. If a patient is randomized but never receives treatment, the patient will be considered enrolled in the study. The randomization slot will not be re-allocated to a new patient due to the intent-to-treat nature of the study.

b. Method for notifying investigator of intervention allocation

Randomization will take place only if the patient has met the eligibility criteria and has completed the baseline evaluation. The site investigators will be provided a 24-hour toll free number that will connect to the centralized IVRS.

D. Intervention

Overview of treatment arms: All patients will receive a kit containing metformin XR/placebo or clomiphene citrate/placebo. The active dose of metformin XR will be

NICHD Reproductive Medicine Network
 PPCOS-Pregnancy in Polycystic Ovary Syndrome Protocol

500 mg/tablet consisting of an extended-release tablet given on a two tablets twice per day dosing regimen. The active dose of clomiphene citrate will be 50 mg/tablet, consisting of a generic form. Both investigators and patients will be blinded to the individual contents of the medication kit. Progesterone levels will be obtained at weekly visits. A treatment cycle will consist of either

- 1) an ovulatory response to medication, as determined by weekly progesterone levels followed by either pregnancy or withdrawal bleed, or
- 2) an anovulatory response consisting of 5 consecutive weeks of non-ovulation as determined by weekly serum progesterone levels.

The maximum duration of the study will be six treatment cycles, or 30 consecutive weeks on study drug. If the 6th treatment cycle begins prior to 30 weeks on study drug, the 6th cycle may be completed.

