completed, an Investigator or designee will call the IVRS in order to randomize a patient into the trial. The IVRS will query the site for patient eligibility information. If the patient is eligible, the site will be provided with a patient identifier and a study kit number. The Study Coordinator at each site will be responsible for storing, dispensing, and performing pill counts on the study medication.

In the event that emergency unblinding is needed, only the site PI will be able to unblind a patient to treatment by calling the IVRS system. The site PI and DCC staff will receive notification from the central randomization service when emergency unblinding has occurred. With the exception of emergency unblinding, patients will not be unblinded until study findings are released.

F. Study Specific Procedures and or Visits

The screening visit and procedures in the baseline visit are described above under E.3 Assessment of Eligibility: The weekly/monthly monitoring visits are described below.

Description of Weekly/Monthly Visits:

Patients will follow-up weekly after beginning medication. Ideally, the patient will be seen the same day each week, but the weekly visit can take place 4-12 days after the previous weekly visit. A serum progesterone level will be sent weekly and urinary hCG screen as necessary (for example suspected pregnancy, two consecutive positive ovulatory progesterone levels, or one positive level with a missed previous visit, or no menses for 5 weeks). Case report forms (CRFs) will be filled out on a monthly basis. Pelvic exam and/or ultrasound will be performed at the discretion of the principal

NICHD Reproductive Medicine Network
PPCOS-Pregnancy in Polycystic Ovary Syndrome Protocol

investigator. A pill count will be obtained once a month. Medication will be dispensed by the nurse coordinator or appropriate person on a predefined basis.

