The weekly visit does not necessarily have to take place on site. It may be accomplished off site by the nurse coordinator at a home or office visit, or at a commercial lab with overnight delivery of the serum specimen to the site laboratory, or at another clinical laboratory with results forwarded to the RMN site. This will facilitate the enrollment of subjects who are at a greater distance from one of the study sites. The progesterone level must be reviewed, however, on a weekly basis by study personnel. Weekly phone or e-mail contact between study personnel and patients is encouraged, however, to increase compliance. Urinary pregnancy tests may also be dispensed to patients who may miss a weekly visit to detect pregnancy.

A patient should be seen in person by study personnel, at a minimum, every four weeks. The monthly visit can be conducted 24-37 days after the previous monthly visit, or in the case of Monthly Visit 1, after the start of study drug. This visit will be performed after an overnight fast. This visit will be important not only to monitor adverse events or side effects, but also to perform pill count, review bleeding and intercourse diaries, dispense medication, obtain a weight and waist to hip ratio, and to draw blood. At this visit it is also important to obtain the serum from a 7.5cc red top in order to examine circulating response variables in the core lab. Blood may also be obtained for the weekly progesterone level at this visit.

Missed Visits:

It is anticipated that subjects may miss a weekly visit from time to time due to schedule conflicts. Missing two consecutive weekly visits becomes more problematic as a potential ovulation may be missed. In this case the P.I. can base further management on

NICHD Reproductive Medicine Network
PPCOS-Pregnancy in Polycystic Ovary Syndrome Protocol
the clinical situation (i.e. no menstrual bleeding and continued anovulatory progesterone levels or subsequent menstrual bleeding and presumptive ovulation.) Missing three consecutive visits may be justification for excluding the patient from further study. This will be determined by the site P.I. after consultation with the DCC.

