Non-response will be defined as the lack of an elevated progesterone level for any consecutive five week treatment period during the study. If the patient fails to respond to treatment for any five week period, they will be instructed to increase their clomiphene citrate dose after the fifth anovulatory progesterone level to two pills a day for five days while continuing the metformin XR tablet at 2 tablets twice per day. Further non-response for five weeks will lead to an increase in clomiphene citrate to three pills a day for five days. This dose will continue until the completion of a total of six treatment cycles or 30 weeks is reached. This may involve more than one five week period with the maximum clomiphene citrate dose of three tablets a day for five days (See Appendix 1: Study flow sheet below).

Induction of Withdrawal Bleeds for Non-Responders:

There will be no induction of withdrawal bleeds for non-responders during the course of the protocol, unless as dictated by the P.I. at the site. The benefits and/or risks of this for short amounts of time (i.e. less than 6 months) have not been well described in the literature. The use and indication for inducing a withdrawal bleed should be noted on the weekly CRF. During the induction of the withdrawal bleed with medroxy

progesterone acetate (5 mg x 10 days), the patient is to continue metformin XR or
RMN Protocol
08Jan2004

NICHD Reproductive Medicine Network
PPCOS-Pregnancy in Polycystic Ovary Syndrome Protocol
placebo, but not take clomiphene citrate or placebo until day 3 of the withdrawal bleed.

If there is no spontaneous withdrawal bleed after the use of medroxyprogesterone acetate, a pregnancy test should be checked prior to clomiphene citrate at an arbitrary “day 3”, preferably within two weeks of completing the medroxyprogesterone acetate.

Breaks in Study Protocol:

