- An ovulation will be defined as an elevated weekly progesterone level separated by at least one week with a nonovulatory progesterone level. A binary variable indication whether the patient ovulated or not will be created for each cycle. Furthermore, cycles to first ovulation will be used as time to event variable.
- Time to pregnancy is defined as the number of cycles required to achieve a viable implantation (detection of fetal heart beat). Weeks from pregnancy to live birth will also be used as a time to event variable for patients who did not have miscarriages.
- Conception. Conception is confirmed by a positive serum hCG value. Cycles to first conception will be used as a time to event variable.

E. Drop outs/Treatment Failures

Dropouts, either by patient choice or physician recommendation due to adverse effects or poor compliance will be analyzed by intention to treat as treatment failures. Subjects who have completed 30 weeks or 6 treatment cycles without a pregnancy will also be considered as treatment failures. Subjects who conceive and are lost to follow up will be considered as a treatment success. It is considered unlikely that the patients will be lost to follow-up after a conception on a treatment regimen.

NICHD Reproductive Medicine Network
PPCOS-Pregnancy in Polycystic Ovary Syndrome Protocol

F. Interim Analysis

Analysis Plan: An interim analysis will be conducted on the primary endpoint when 50% of the study participants have completed treatment. The primary analysis described above will be performed and the O'Brien-Fleming (1979) method will be applied to adjust for at the number of looks at the primary endpoint. The interim analysis should also provide a detailed summary of adverse events reported. The critical value for the primary analysis will be specified in the detailed analysis plan. The results of the interim analysis will be submitted to the Data Safety and Monitoring Committee (DSMC). The interim analysis results will be presented in a blinded fashion to the DSMC, who will then evaluate the findings to determine whether the trial should be continued, modified, or discontinued.

Stopping Rules: The stopping rule for the O'Brien-Fleming method compares the statistic Z_i with $Z^*(N/i)^{.5}$, where Z^* is the critical value for the significance level (.05), N is the total number of analyses ($N = 2$) and i is the analysis number (for the one planned analysis, $i = 1$).

VI. DISCLOSURE OF DATA

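### Ovulation is scored from weekly progesterone alone, so a cycle with a confirmed conception can be recorded as not ovulated

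*Protocol*

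**What the plan says.** The endpoint is set in Protocol V.C, Definition of Secondary Measures: "An ovulation will be defined as an elevated weekly progesterone level separated by at least one week with a nonovulatory progesterone level". The next sentence adds: "A binary variable indication whether the patient ovulated or not will be created for each cycle". The same list confirms conception by serum hCG, with no reference to progesterone. Ovulation rate and cycles to first ovulation are secondary efficacy parameters in the Synopsis, and secondary hypothesis 5 (III.C) concerns ovulation.

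The treatment rules also rest on progesterone. IV.D allows two kinds of treatment cycle: one that is ovulatory by weekly progesterone and ends in pregnancy or a bleed, and "an anovulatory response consisting of 5 consecutive weeks of non-ovulation as determined by weekly serum progesterone levels". IV.F, Nonresponders, says: "Non-response will be defined as the lack of an elevated progesterone level for any consecutive five week treatment period during the study". Under IV.F, Responders, a single weekly level of at least 5 ng/mL is enough.

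On sampling, IV.F says that "the weekly visit can take place 4-12 days after the previous weekly visit". Under Missed Visits it concedes: "Missing two consecutive weekly visits becomes more problematic as a potential ovulation may be missed". The investigator may then manage the woman on the clinical picture, one version of which is "subsequent menstrual bleeding and presumptive ovulation". IV.F also provides: "Urinary pregnancy tests may also be dispensed to patients who may miss a weekly visit to detect pregnancy". Breaks from clomiphene of up to four weeks are allowed, with home pregnancy tests for weekly checks.

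**The concern.** A two-valued score with one route to yes works only if every cycle is sampled often enough to catch the progesterone rise. The protocol expects that this will sometimes fail, and it provides a second way of detecting conception in just those weeks. The ovulation definition does not use that second source, so two secondary endpoints defined in the same list can contradict each other for the same cycle.

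What is at stake is the ovulation rate and cycles to first ovulation. An ovulation that leaves no elevated sample can only lower the recorded rate and delay the recorded first ovulation. V.C hopes the secondary results will help to power future studies, so an understated rate could be carried forward.

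**Working it through.** **1. One record taken through the rules.** A woman has a low progesterone level, misses her next visits, tests positive at home, and serum hCG confirms it. Study drug stops when hCG is detected (IV.F, Responders).
- Conception (V.C): yes, on serum hCG.
- Ovulation in that cycle (V.C): no elevated weekly level exists, so the condition for yes is not met.
- Cycle type (IV.D): not ovulatory by progesterone, and not five weeks of measured non-ovulation. It fits neither type.

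This contradiction follows from the text and needs no outside figure. It requires that no elevated sample was drawn before drug stopped. IV.F lists suspected pregnancy and five weeks without menses among the triggers for hCG testing, so a test need not follow an elevated level.

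**2. How many ovulations might go unrecorded.** The protocol gives no figure to reproduce; the sample size in IV.B uses live-birth rates. Two inputs must be assumed:
- m, the chance that a weekly sample is missed, independently each week. Not in the protocol; range 5-30%.
- k, the number of weekly samples that would be elevated around one ovulation, 1 or 2. IV.F, Responders, says that two weekly levels may straddle the peak.

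Share unrecorded = m^k:

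| m | k = 1 | k = 2 |
|---|---|---|
| 5% | 5% | 0.25% |
| 10% | 10% | 1% |
| 20% | 20% | 4% |
| 30% | 30% | 9% |

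Between these cases, suppose progesterone stays at or above 5 ng/mL for L days after an ovulation without conception (assumed, 8-9 days), with visits exactly 7 days apart. One visit falls in the window with probability (14 - L)/7 and two with probability (L - 7)/7. At m = 10%:
- L = 9: (5/7)(0.10) + (2/7)(0.01) = 0.074
- L = 8: (6/7)(0.10) + (1/7)(0.01) = 0.087

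So about 7-10% go unrecorded if usually one sample would be elevated, and about 1% if two would be. As an illustration, IV.B uses a 48% ovulation rate from the combination arm of a cited randomised trial. At m = 10% it would be recorded as 0.48 × 0.99 = 47.5% or 0.48 × 0.90 = 43.2%.

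**3. If missed visits differed between arms.** With a true rate of 48% in both arms and m of 5% against 20%, the spurious difference is 0.48 × (0.20 - 0.05) = 7.2 points for k = 1, and 0.48 × (0.04 - 0.0025) = 1.8 points for k = 2.

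**4. A check on an obvious remedy.** Suppose cycles with sampling gaps were dropped only when nothing positive was found. Assume a true rate of 48%, gaps in 20% of cycles, and half the ovulations in gap cycles detected. Detected ovulations are 0.80 × 0.48 + 0.20 × 0.48 × 0.5 = 0.384 + 0.048. Cycles kept are 0.80 + 0.048. The rate becomes 0.432/0.848 = 51%, which is too high. Gap cycles must not be kept or dropped according to their result.

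**The case against.** The strongest reply is that the protocol never says how unsampled weeks are scored. A reader might infer that they count as observed non-ovulation. The yes/no wording and the non-response definition invite that, but no section states it. IV.D speaks of non-ovulation determined by weekly levels, and IV.F raises the dose after a fifth anovulatory level; both imply measured values. A missing-sample rule may also sit in the analysis plan, which is not at hand. This stands, and the point does not rest on that inference. It rests on the definition the protocol does fix, which leaves out hCG.

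A reader might also infer that menses after a gap shows ovulation. The protocol calls this only presumptive and offers it for management. It also permits progestin-induced bleeds (IV.F, IV.H). Keeping a biochemical endpoint apart from site judgement is a legitimate choice.

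Larger losses can be produced. If visit gaps were spread evenly over 4 to 12 whole days (mean 8), the share of ovulations falling wholly between visits with full attendance would be [(1+2+3)/9]/8 = 8.3% for L = 9 and [(1+2+3+4)/9]/8 = 13.9% for L = 8. Nothing supports an even spread: IV.F calls the same day each week ideal and allows off-site sampling to help attendance.

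Finally, one might infer a bias against metformin through gastrointestinal side effects. No section links those effects to missed visits, so this is conjecture.

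**Conclusion.** The point holds in a limited form. The ovulation endpoint is fixed on weekly progesterone alone and can therefore contradict the hCG-based conception endpoint for the same cycle. It also makes no provision for the missed ovulations that IV.F acknowledges.

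The reach is small. Ovulation rate and cycles to first ovulation are exploratory and unpowered by the protocol's own statement. The live-birth analysis and the sample size are untouched.

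The size cannot be fixed from the document. The 1% and 7-10% figures assume 10% of weekly samples missed, independently; the 7% end also assumes a 9-day window and exact weekly visits. Runs of missed weeks would do more harm than independence suggests. These figures describe ovulations in general. How often a conception would fall in a cycle scored as not ovulated is not estimated, and such cases may be few. The documents do not establish a direction of bias between arms.

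**What to change.** In V.C, score a cycle as ovulated if it has an elevated progesterone level or a serum-hCG-confirmed conception, and align the description of a treatment cycle in IV.D for counting purposes. This changes scoring only, not management.

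Add a sensitivity analysis restricted to adequately sampled cycles. Adequacy should be defined from visit dates alone, be compatible with the permitted 4-12 day window (for example, no interval between progesterone samples longer than 12 days), and apply whatever the progesterone or hCG result. This avoids the distortion in step 4. It also serves as a check on the main rule, which recovers only those unsampled ovulations that led to conception. The text should say how cycles to first ovulation is handled when an early cycle is inadequately sampled.

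Optionally, add a second sensitivity analysis that counts the presumptive ovulations of IV.F as ovulated, excluding progestin-induced bleeds.

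The cost is a few sentences and a little extra analysis. Visit dates, progesterone levels, hCG results and bleeding diaries are already collected. The restricted analysis loses some precision.
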